Preliminary analysis of aggregated data from the WELC Integrated Care Programme (using the Data Cube) suggests that the pool of potential matches is sufficiently large to select matched controls within cluster (*i.e.*, geographically clustered GPs) and within the same risk-band (top 0.5%, 0.5-5%, or 5-20%). This is because enrolment rates at cluster level vary between 17% and 38%, and enrolment rates for the different risk-bands are 50%, 24% and 2%, respectively.

Matching will be done to optimise the similarity of integrated care and matched control groups with respect to variables that are likely to be predictive of the endpoints. These variables will include:

predictive risk score; age; gender; ethnicity; prior primary and secondary care utilisation; a measure of socioeconomic deprivation (the Index of Multiple Deprivation, attributed to the Lower Super Output Area of residence); existing diagnoses of health care conditions; and numbers of prescription medications. Many of these variables feature in the Combined Predictive Model (Wennberg et al. 2006), but are included in our matching algorithm so that the groups will be similar in terms of these more detailed variables as well as the overall risk score.

To increase the number of potential controls available for the analysis, we will assign each potential control up to 12 index dates, one for each month from January 2014 to December 2014, assuming that the patient is alive at each of these time points. Baseline variables (*e.g.*, age and prior primary and secondary care utilisation) will then be calculated at each of these index dates, and each control patient will provide the matching algorithm with up to twelve observations.

Matched control observations will be selected using the genetic matching algorithm, which is a computer-intensive search procedure that produces more closely balanced groups than traditional approaches such as nearest neighbour matching on the propensity score (Sekhon & Grieve 2012). Balance will be assessed using the standardised difference, which is defined as the difference in means as a proportion of the pooled standard deviation (Austin 2009). Although the standardised difference would ideally be minimised without limit, a threshold of 10% has been used to describe meaningful difference (Normand et al. 2001). We will adjust the parameters in the genetic matching algorithm until we obtain standardised differences below these thresholds.

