The matching will be conducted with replacement, meaning that a patient might be used as the control for multiple integrated care patients. Our preference is to select two control observations per patient, as this would increase the precision of our estimates of the effect of the integrated care pathway on patient outcomes (*i.e.*, reduce the width of our confidence intervals, meaning we can be more sure about the effect size). However, if it is not possible to obtain adequate balance when selecting two controls per patient, we will rerun the matching algorithm when selecting one control per patient.

Statistical method

After adequate balance has been obtained, we will estimate the effect of the integrated care pathway on patient outcomes by fitting regression models to the data. These models will adjust for residual differences remaining between the groups in the baseline variables after matching. We will include all patients in these analyses, even if they died or moved away from the WELC area during the 12-month follow-up period.

For our primary endpoint, number of emergency hospital admissions, use of Poisson regression seems appropriate, but depending on the empirical distribution of this endpoint, alternative distributions will be considered (*e.g.*, negative binomial). We assume that ordinary least squares (linear) regression will be used

for our secondary endpoint, the number of hospital bed days. On receipt of the line-level data, we will test the suitability of these assumptions, and consider alternative distributions if appropriate. We will follow a similar procedure for other endpoints making sure that assumptions on distributions are appropriate.

Subgroup analysis

The main analysis will be pooled across all three CCGs and across all risk bands, as this approach is necessary to ensure adequate sample size. However, we will also examine whether there is evidence that the integrated care pathway affected the outcomes of certain subgroups of patients more or less than average. Specifically, we will examine subgroups defined by CCG (Newham, Tower Hamlets, and Waltham Forest) and risk band (top 0.5%, 0.5-5%, and 5-20%). We will also distinguish between patients with and without a recorded mental health condition.

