The subgroup analysis will be performed using interaction tests, and interpreted using credibility criteria (Sun et al. 2012). To determine whether subgroups were differentially affected by the intervention, we will compare confidence intervals from the interaction tests with the estimated effect from the pooled analysis.

Secondary analysis will also include the evaluation of health care utilisation for patients at the end of life, and evaluation of the whole cohort but accounting for attrition due to patients leaving the programme, dying, or moving out of the WELC area. Attrition will be dealt with using appropriate statistical methods, effectively using a 'person-years' denominator (this can be operationalised by using an offset term in the Poisson regression).

Sensitivity analysis for unobserved confounding

One of the main threats to the validity of this study is unobserved confounding. That is, although we anticipate that the intervention and matched control groups will be similar in terms of observed variables (such as age and prior number of hospital admissions), there may be differences between these groups that we do not observe (such as social isolation). Our findings might be biased if, for example, the patients recruited into the integrated care pathway were disproportionately isolated, and these patients were expected to have worse outcomes than other patients. We note that such selection effects would need to occur beyond the formal eligibility criteria for the integrated care programme, because the formal criteria should be exactly reproducible using the routine data (predictive risk score). However, health care professionals might have had a tendency to enrol patients with some characteristics more than others, and likewise some patients might have been more or less willing to consent to be enrolled than others.

Although there is no definitive way to assess the effect of unobserved confounding, we can compare the mortality rates of the integrated care and matched control groups (West & Thoemmes 2010). On the assumption that the integrated care pathway is unlikely to have had a large positive or negative impact on

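### Balance is judged only for the whole groups, so the interaction test by mental health condition can rest on strata that fail the plan's own 10% rule

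*Protocol*

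**What the plan says.** All of this is in the Methods of the protocol.

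- **Control group, aim of the match.** "Matching will be done to optimise the similarity of integrated care and matched control groups with respect to variables"; the variables meant are those expected to predict the endpoints. Diagnoses enter this list generically: "existing diagnoses of health care conditions; and numbers of prescription medications". Mental health is not singled out.
- **Control group, strata.** Preliminary aggregate data suggest that "the pool of potential matches is sufficiently large to select matched controls within cluster" and within risk band. This is a statement of feasibility. Mental health status is not mentioned there.
- **Control group, acceptance rule.** The threshold cited is a standardised difference of 10%, and "We will adjust the parameters in the genetic matching algorithm until we obtain standardised differences below these thresholds". No level below the whole groups is given.
- **Control group, replacement.** "The matching will be conducted with replacement, meaning that a patient might be used as the control for multiple integrated care patients".
- **Statistical method.** Modelling starts once balance is adequate, and "These models will adjust for residual differences remaining between the groups in the baseline variables after matching".
- **Subgroup analysis, subgroups.** These are CCG, risk band and mental health condition; the last is stated as "We will also distinguish between patients with and without a recorded mental health condition".
- **Subgroup analysis, test.** On how all three are to be judged, the section adds: "The subgroup analysis will be performed using interaction tests, and interpreted using credibility criteria".

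**The concern.** A standardised difference for the whole sample is a weighted average of the differences in its parts. Opposite-signed differences in patients with and without a mental health condition can cancel, and a large difference in the smaller group can be diluted. An enrolled patient with a mental health condition may also be matched to a control without one. Once the sample is split by that flag, the subgroup contrast is then no longer the matched contrast.

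The protocol gives a reason to expect selection of this kind. Its section on unobserved confounding accepts that professionals may have favoured some patients for enrolment and that willingness to consent may vary. Either could differ by mental health status.

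At stake is a statement about who benefits more or less. A clean overall balance table would give no warning that this comparison was less well balanced than the main one.

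**Working it through.** **The plan's own figure.** The Sample size calculation uses a mean of 0.6, an SD of 1.4, a 15% change (0.15 × 0.6 = 0.09), two-sided 0.05 and 90% power. The normal approximation for 1:1 is n per group = 2 × (1.960 + 1.2816)² × 1.4² / 0.09² = 5,085.06, rounded up to 5,086, a total of 10,172. With two controls per patient the total is 3 × 3,814 = 11,442. The noncentral t version gives exactly the stated 10,174 and 11,445. These figures are sound; the point concerns bias in a subgroup contrast.

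**Step 1: what the pooled rule allows.** Let p be the share with a mental health condition, taken as equal in both arms, with a common SD:

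pooled difference = p × d(MH) + (1 − p) × d(rest), so d(MH) = [pooled − (1 − p) × d(rest)] / p.

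The protocol does not give p; 20% and 30% are assumed.

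| Pooled | d(rest) | d(MH), p = 20% | d(MH), p = 30% |
|---|---|---|---|
| 0 | −0.10 | 0.08/0.20 = 0.40 | 0.07/0.30 = 0.23 |
| 0.10 | 0 | 0.10/0.20 = 0.50 | 0.10/0.30 = 0.33 |

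These are limits of what the rule permits, not forecasts.

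**Step 2: a more ordinary case.** A null simulation had the flag as one matching variable, 20% prevalence, and enrolment depending on prior admissions differently by mental health status (all assumed). The difference in prior admissions was about 0.19 in the mental health group, 0.05 to 0.08 in the rest and about 0.11 pooled. The identity gives 0.2 × 0.19 + 0.8 × 0.05 = 0.078 to 0.2 × 0.19 + 0.8 × 0.08 = 0.102. It is only approximate here, because it assumes equal shares and a common SD. The pooled value sits at about the threshold while the mental health group is at nearly twice it.

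**Step 3: false interaction without adjustment.** For a covariate with log rate ratio b per SD in both strata and no true effect, the false interaction ratio is exp{b × [d(MH) − d(rest)]}. With b = 0.4 (assumed):

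- Step 2 values: exp(0.4 × 0.11) = 1.045 to exp(0.4 × 0.14) = 1.058.
- p = 20%, d(MH) = 0.20, d(rest) = −0.05: exp(0.4 × 0.25) = 1.105.

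A simulation with 6,360 per arm, mean 0.6, SD 1.4, Poisson models with robust standard errors, pooled difference 0 and 400 runs per scenario gave 1.102 for the second case. Across p of 20% and 30%, with and without an extra slope of 0.2 per SD in the mental health group:

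| d(MH) | False ratio, unadjusted | False-positive rate |
|---|---|---|
| 0.1 | 1.05 to 1.09 | 8 to 16% |
| 0.2 | 1.10 to 1.16 | 15 to 41% |
| 0.3 | 1.16 to 1.27 | 28 to 78% |

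**Step 4: with the planned adjustment.** In the same simulation with the covariate as a main effect:

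- Equal slopes: ratio 0.995 to 1.005, false positives 3 to 6%.
- Extra slope of 0.2 per SD in the mental health group: ratio 1.01 to 1.04, false positives 5 to 7%.
- Covariate-by-mental-health term added: ratio 0.995 to 1.006, false positives 3 to 7%.

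Monte Carlo error on a 5% rate is 1.96 × √(0.05 × 0.95 / 400) = 2.1 percentage points, so these rates are close to nominal. In the Step 2 setting the adjusted ratio was about 0.96 to 1.03.

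**Step 5: less favourable models.** Here prior admissions were skewed counts entered as a linear term, d(MH) was ±0.2 to 0.3, p was 20 to 30%, and there were 200 runs per scenario:

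- Correct form, equal slopes: ratio 0.99 to 1.01, false positives 3 to 6%.
- True effect on log(1 + prior), equal slopes: 0.95 to 1.00, 4 to 11%.
- The same with a steeper mental health slope: 0.87 to 1.03, 7 to 31%.
- Linear form with the mental health slope doubled (a strong assumption): 0.78 to 1.16, 9 to 63%.

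**The case against.** The strongest objection is that the plan already adjusts for baseline differences after matching, and Step 4 shows that this removes nearly all of the false interaction from measured covariates when the model is about right. That stands, and it sets the size of the point. What it leaves open is Step 5: the protocol promises to check distributions, but not functional form or slopes that differ by subgroup.

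A second objection is that the exact-match list and balance tables usually belong in a statistical analysis plan. That is partly right: silence on mental health status does not rule out matching on it. But the protocol itself fixes the balance rule, the point at which modelling starts and the subgroups, and the rule as fixed does not cover the subgroups.

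Third, the main analysis is pooled and subgroup results are read with credibility criteria. This limits the consequence. However, the reference list shows that those criteria come from a review of randomised trials, and the protocol does not say that they cover balance after matching.

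A reader might infer three stronger things that the documents do not support.

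- **That the CCG and risk-band subgroups are exact by construction and only mental health is exposed.** Selection within cluster and risk band is only said to be feasible. Even an exact match on a stratum does not balance the other covariates inside it, so all three subgroups need the same check.
- **That large false interactions survive adjustment.** A simulation with nearest-neighbour matching gave adjusted ratios of 0.94 to 1.20, but the protocol specifies genetic matching because it expects closer balance, so that range does not describe this design.
- **That an exact match on the flag is the remedy.** It changed little in the Step 2 setting. In the top 0.5% risk band, where 50% are enrolled, there is about one unenrolled patient per enrolled patient (0.50/0.50) before any split by cluster or mental health status. Monthly index dates and replacement relieve this only in part.

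**Conclusion.** The point holds as a limited, inexpensive improvement. The pooled 10% rule does not protect the mental health contrast: differences of about 0.19 in that group against 0.05 to 0.08 in the rest can sit under a pooled value near the threshold. After the planned adjustment, the false interaction ratio is roughly 0.96 to 1.04 under modest assumptions, small beside the 15% change on which the study is powered. It reaches 0.87 with a wrong functional form and a steeper slope in the mental health group, and goes further only under a doubled slope.

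The conclusion that the rule leaves a gap follows from the text and the identity in Step 1. The sizes rest on assumed prevalence, covariate strength, enrolment pattern and slopes, none of which the protocol gives. The primary pooled estimate is not affected.

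**What to change.** Add to the Subgroup analysis section, to be done before any interaction model is run:

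1. Tabulate standardised differences within each level of every pre-specified subgroup (CCG, risk band, mental health condition) and apply the 10% threshold there.
2. Where a level fails, re-match within that level for the subgroup analysis only, leaving the primary match as it is.
3. In those cases, include covariate-by-subgroup terms in the interaction model, at least for the variables that fail.

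Exact matching on the mental health flag at the index date is optional where the control pool allows it. It should not be imposed on the primary match in sparse cells, chiefly the top 0.5% band, where it could worsen balance on other variables for the primary endpoint.

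The cost is extra balance tables, possibly a second matching run for some levels, and slightly wider subgroup intervals. No new data are needed.

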Our primary endpoint is the number of emergency hospital admissions per patient, which is a commonly used endpoint in evaluative studies of integrated care. Our secondary endpoint is the number of hospital bed days per patient over twelve months, as this reflects changes to the length of stay in hospital as well as the number of admissions.

Other endpoints will be the notional cost of care per patient, including primary and secondary care cost and other indicators listed above.

Sample size calculation

Our sample size will be sufficient to identify a 15% change in emergency admissions between the enrolled patients and the matched control group. Our sample size calculation was performed in SAS with 90% power and a two-sided p-value of 0.05. We assumed an average number of emergency admissions per patient per year of 0.6 with a standard deviation of 1.4. These assumptions are based on a previous study with a similar population base (Steventon, Bardsley, Billings, Dixon, et al. 2012).

The sample size calculation indicate that in order to identify a 15% change in emergency admission a sample size of 10,174 is required in case of a balanced sample (1 control per enrolled patient), or 11,445 in case of a sample with two controls per enrolled patient. In comparison, we estimate that our study will include at least 6,360 integrated care patients. In a matched control design with one control patient per integrated care patient, the total sample size would therefore be 12,720 patients. If there were two control patients per integrated care patient, the total sample size would be higher, at 19,080.

Control group

In the absence of a randomised controlled trial, we will compare the outcomes of the integrated care cohort with a retrospectively matched control group. In other words, line-level routine, patient information will be used to characterise the integrated care patients as well as possible, and then select, for every patient, matched controls that were not enrolled onto the programme but had similar observed characteristics to the enrolled patient. These matched patients will form the control group for the evaluation of the programme.

Control patients will be registered with a general practice in the WELC area, and will not have been enrolled onto the integrated care pathway at any point before the end of our follow-up period.

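### The subgroup rule sets the interaction's confidence interval against the pooled effect, but the reference value for an interaction is no interaction

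*Protocol*

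**What the plan says.** In the Protocol, Subgroup analysis, the question is "whether there is evidence that the integrated care pathway affected the outcomes of certain subgroups of patients more or less than average". The subgroups are CCG (three levels), risk band (three levels) and presence or absence of a recorded mental health condition (two levels).

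The method is then given: "The subgroup analysis will be performed using interaction tests, and interpreted using credibility criteria". The next sentence supplies the decision rule. Its purpose is "To determine whether subgroups were differentially affected by the intervention", and its content is "we will compare confidence intervals from the interaction tests with the estimated effect from the pooled analysis". The Protocol nowhere states the value that stands for no interaction.

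The inputs for sizing the problem are in Sample size calculation. The study should "identify a 15% change in emergency admissions between the enrolled patients and the matched control group", with "90% power and a two-sided p-value of 0.05", a mean of 0.6 emergency admissions per patient-year, an SD of 1.4 and at least 6,360 enrolled patients.

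**The concern.** An interaction term measures how far the effect in one subgroup differs from the effect in another. If the pathway works equally well everywhere, the interaction is null whatever the pooled effect is. Comparing its interval with the pooled effect therefore asks whether the difference between subgroups is as large as the overall effect, which is not the question posed.

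Taken literally, the rule can read a uniform benefit as heterogeneity, and can read a real interaction of about the size of the pooled effect as no difference. The Executive summary wants results in time for operational decisions. The Handover section foresees reuse of the code monthly or quarterly, with subgroup results by risk score or CCG, so a misdefined rule could be carried forward.

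**Working it through.** **Inputs.** Mean 0.6, SD 1.4, two-sided 0.05, 90% power, 15% change (0.15 × 0.6 = 0.09 admissions) and 6,360 enrolled, all from Sample size calculation. Subgroup shares are not given. Equal shares and 1:1 matching are assumed unless stated otherwise, with a normal approximation.

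**1. The Protocol's own figure.** n per group = 2(1.960 + 1.282)² × 1.4² / 0.09² ≈ 5,086, a total of 10,172 (stated: 10,174). With two controls per enrolled patient the total is 11,442 (stated: 11,445). Both are reproduced within rounding, so the inputs are read correctly.

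**2. Standard errors on the log rate-ratio scale.** For a subgroup with n enrolled, s = √(2 × 1.4² / (n × 0.6²)). The interaction between two such subgroups has SE_int = s√2. The pooled estimate has SE_P = 0.0414.
- Three equal subgroups, n = 2,120: s = 0.0717, SE_int = 0.1014 (one pair of subgroups).
- Two equal subgroups, n = 3,180: s = 0.0585, SE_int = 0.0828.

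**3. Literal rule, no true interaction.** The rule flags when |interaction − pooled estimate| > 1.96 × SE_int. With equal shares the two estimates are uncorrelated, so their difference has SD √(SE_int² + SE_P²): 0.1095 for three subgroups, 0.0925 for two. At a pooled rate ratio of 0.85 its mean is −ln 0.85 = 0.1625.
- Three: Φ((−0.1987 − 0.1625)/0.1095) + 1 − Φ((0.1987 − 0.1625)/0.1095) = 0.37.
- Two: the same formula with 1.96 × 0.0828 = 0.162 gives 0.50.

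| Pooled rate ratio | False flags, three subgroups | False flags, two subgroups |
|---|---|---|
| 0.85 | 37% | 50% |
| 0.90 | 20% | 27% |
| 0.95 | 10% | 13% |
| 1.00 | 7% | 8% |

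The test against no interaction gives 5% in every cell.

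**4. Literal rule, true interaction equal to the pooled effect (ln 0.85).** The mean of the difference is now zero, so the rule flags only 7% (three) or 8% (two) of the time. The ordinary test has power of about Φ(0.1625/0.1014 − 1.96) = 36% for three and Φ(0.1625/0.0828 − 1.96) = 50% for two.

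**5. Unequal shares, one subgroup against the rest, difference scale, pooled effect −0.09.** With no interaction, the literal rule flags 45%, 41%, 20% and 13% of the time at subgroup shares of 50%, 33%, 10% and 5%. With two controls per patient the figures are 55%, 50%, 25% and 16%. The rule also depends on direction: at 1:1 and a 50% share it flags an interaction of −0.09 in 8% of cases and one of +0.09 in 93%, where the ordinary test has 44% for either.

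**6. Alternative reading: each subgroup's own interval against the pooled estimate.** The subgroup forms a share f of the pooled estimate, so the difference has SD s√(1 − f), and the false-flag rate per subgroup is 2(1 − Φ(1.96/√(1 − f))): 1.6% at one third, 0.6% at one half. On the difference scale at 1:1:

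| Setting | False flags, this reading | False flags, interaction test | Power for 0.09, this reading | Power for 0.09, interaction test |
|---|---|---|---|---|
| Two equal levels | 0.6% | 5.0% | 17% | 44% |
| Three equal levels, any level flagged, one level differing | 4.3% | 5.0% (joint) | 29% | 31% (joint) |

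The three-level row was simulated with 1,000,000 replicates.

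**The case against.** The strongest defence is that the authors meant something else. They ask whether the pathway "affected the outcomes of certain subgroups of patients more or less than average", which points to subgroup-specific effects set beside the pooled one. On that reading there are no excess false flags, and with three equal levels, the number both CCG and risk band have, little power is lost. The sentence before the rule already names interaction tests, whose null is no interaction. Credibility criteria are also to be applied, and the Handover section wants findings triangulated and the reasons for subgroup variation understood. All of this stands. It does not repair the rule, because the sentence as written still refers to intervals from the interaction tests.

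The figures also rest on assumptions. Equal shares appear nowhere in the Protocol. The footnote in Data specification limits the data to two CCGs, so the three-subgroup figure may not apply to CCG. Two controls per patient are preferred over one (Control group). Matching with replacement and covariate adjustment are ignored.

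A reader might infer that the plan will in any event report subgroup differences that do not exist. The documents do not support that: it needs both the literal reading and a sizeable pooled effect. Nor do they support the inference that the alternative reading misses real differences generally; a material loss is shown here only for a two-level factor.

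**Conclusion.** The decision rule is wrongly stated and should be corrected. Read literally, at the 15% reduction for which the study is sized, its false-flag rate is about 37% (three equal subgroups) or 50% (two) instead of 5%, and it detects an interaction equal to the pooled effect 7-8% of the time instead of 36-50%. The excess of false flags shrinks with the pooled effect, to 7-8% when there is none, and with small subgroups (13% at a 5% share). Read as subgroup-specific intervals, the rule is conservative, with a clear cost only for a two-level factor such as mental health (17% against 44% at equal shares). The Protocol does not settle which reading applies, and on neither reading is the rule a 5% test of interaction.

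The percentages depend on the assumed shares, 1:1 matching and the normal approximation; the choice of reference value does not. A reader might take this as a threat to the trial's main conclusion. It is not: the main analysis is pooled, the subgroup analysis is secondary, and the primary result is unaffected.

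**What to change.** Replace the sentence on comparing intervals with wording such as: *Evidence of a differential effect will be judged by the treatment-by-subgroup interaction against its null value (ratio 1, or 0 on the difference or log scale), using a joint Wald or likelihood-ratio test for factors with three levels. The interaction estimate and its 95% confidence interval will be reported. Subgroup-specific effects will be shown descriptively beside the pooled effect.*

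The cost is one sentence. Interaction tests are already planned, so no further data or models are needed. Even the correct test has modest power here (44% for a 0.09 difference between two equal halves at 1:1), so a non-significant interaction should not be reported as evidence of equal effects.
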